6.7 End-of-Treatment and End-of-Trial Evaluations

Subjects will be free to discontinue trial participation at any time. The investigator will also discontinue any subject from the trial if, in the investigator's opinion, it is not safe for the subject to continue. The date the subject is withdrawn from a treatment and/or from the trial and the reason for discontinuation will be recorded on the CRF.

Trial participation will be considered completed if the subject has met the following trial requirements:

• Has received four CEUS exams during infusion of Optison combined with flash/replenishment imaging of the radioembolized HCC mass if enrolled in the experimental group.

• Has provided informed consent to share liver function, imaging, and outcomes data if enrolled in the control group.

If a subject's participation in the trial is interrupted for any reason (e.g., because of an AE) and the subject has met the criteria described above for completing the trial, the subject's trial participation will be considered completed. If a subject's trial participation is interrupted for any reason by the subject's or investigator's choice and the subject has not met all of the criteria listed above, then the subject will be considered a discontinued subject.

Findings from this study will be submitted in abstract form to the annual meetings of the American Institute of Ultrasound in Medicine, the Radiological Society of North American, and the Society of Interventional Ultrasound. A manuscript detailing study findings will also be submitted to either a radiology or cancer journal.

7. DATA MANAGEMENT AND STATISTICAL ANALYSES

7.1 Data Management

Data forms will be completed for all subjects enrolled in the trial. The subject study files will be stored in a secure file cabinet and maintained by the research study coordinator. Subject study files will be kept for 7 years after the completion of the study. The final data will be entered into a database. The investigator will be responsible for management of the database. The database will be maintained within an organized and secure directory system.

Findings from this study will be submitted in abstract form to the annual meetings of the American Institute of Ultrasound in Medicine, the Radiological Society of North American, and the Society of Interventional Ultrasound. A manuscript detailing study findings will also be submitted to either a radiology or cancer journal.

7.2 Statistical Analyses

Qualitative findings regarding treatment response will be generated by two radiologists based on mRECIST criteria at 1 and 3-4 months post treatment (using the patient's clinically scheduled contrast-enhanced MRI or CT exams). In the event of conflicting outcome reports, outcomes will be evaluated in consensus.

All statistical analysis will be performed by [name] (SKCC Biostatistics Core and faculty member) using SAS version 9.4 (Cary, NC). Aim 1: The primary hypothesis that UTMD improves the effect of

radioembolization on tumor response in HCC patients will be tested with a non-parametric Mann-Whitney U-test of the difference in response distributions between control (radioembolization alone) and experimental group (UTMD + radioembolization), measured at 3-4 months post treatment. The outcome variable in this analysis, the mRECIST score, is treated as an ordinal variable in this analysis. **Aim 2:** To test if tumor perfusion measured by CEUS between UTMD pulses predicts HCC response to radioembolization, perfusion will be characterized in terms of contrast replenishment time intensity curves fit with a 2-parameter exponential recovery curve as described above. The relationship between the normalized profusion values from this image processing and the patients' subsequent mRECIST scores in the UTMD + radioembolization group will be evaluated with Spearman's rank order correlation.

7.2.1 Sample Size Calculation

Aim 1: Little is known about the effect of UTMD on radioembolization in humans. When comparing similar groups in our animal studies, we observed relative effect sizes of 0.4 and 0.9 for tumor growth and survival, respectively. These animal study results may not apply directly to humans, but they demonstrate that large effect sizes are plausible for this intervention in subjects with HCC tumors. Under these assumptions, we have determined that a sample size of 52 patients randomized to each group would be needed in order for a Mann-Whitney U-test to have 85% power to detect a similarly moderately large relative effect of UTMD on the mRECIST score (i.e., 0.6) with a 5% type I error rate. A similar analysis is planned to compare mRECIST evaluations between 1 month and 3-4 month MRI to determine if earlier cross-sectional imaging can be used to predict long-term treatment response. Relative effect sizes for LFT, AFP, pathology, blinded reads from SPECT, planar imaging, and time to next treatment are expected to be similarly large and will also be evaluated using appropriate non-parametric or exact tests, and are each subject to the same power considerations as for the primary endpoint. Confounding of the results will be investigated and potential confounders will be included in ordinary least squares (OLS) regression models (or quantile regression models, depending on the adequacy of the data meeting OLS modeling assumptions) of these endpoints. Aim 2: A sample size of 52 would provide a two-sided test having 5% type I error rate at least 80% power to detect a Spearman's correlation of 0.4 or greater in the population. Confounding will also be evaluated for this aim and regression analysis will be considered similarly as described for Aim 1.

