Protocol Title: Ultrasound Microbubble Destruction for Improving Radioembolization Therapy of Hepatocellular Carcinoma

Trial Objectives: The primary objective of this trial is to:

· Characterize the ability of localized ultrasound contrast agent destruction to improve hepatocellular carcinoma (HCC) response to Y90 radioembolization.

The secondary aim of this trial is to:

· determine if contrast-enhanced ultrasound estimated tumor perfusion can reliably predict HCC response to radioembolization 1-14 days post treatment.

Trial Design: This is an open-label, randomized trial that will be conducted at one clinical site to determine if ultrasound-triggered microbubble destruction (UTMD) can be used to improve radioembolization of HCC. The subject population will be patients scheduled for radioembolization of a previously untreated HCC mass at Thomas Jefferson University. Patients will be randomly assigned to either the experimental (UTMD + radioembolization) or control group (radioembolization alone) by the research coordinator using a random assignment generator. For patients assigned to the experimental group, the study will consist of up to three contrast-enhanced ultrasound (CEUS) exams 1-6 hours post radioembolization, and approximately 7 and 14 days post treatment. Treatment response will be evaluated using modified response evaluation criteria in solid tumors (mRECIST) at 1 and 3-4 months post treatment based on the patient's clinically scheduled contrast-enhanced MRI or CT. For patients assigned to the control group, only outcomes data will be collected (without intervention).

Ultrasound imaging will be performed using a state of the art commercial ultrasound scanner with a curvilinear transducer. As part of each CEUS exam, patients will first undergo baseline grayscale B-mode and power Doppler imaging (PDI) of the treated mass. Patients will then receive an infusion of the ultrasound contrast agent (UCA) Optison (GE Healthcare, Princeton, NJ), while being imaged with two-dimensional (2D) dual mode B-mode / coded harmonic imaging. Once the presence of contrast has been confirmed in the tumor, a series of flash-replenishment sequences will be generated to destroy UCA within a region of interest encompassing the tumor. This sequence will be repeated at imaging planes throughout the tumor for the duration of the infusion.

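### Comparing 1-month with 3-4-month mRECIST scores tests for a shift between scans, not whether the early scan predicts the later response

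*Combined protocol and SAP*

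**What the plan says.** Section 7.2 defines the Aim 1 analysis as a "non-parametric Mann-Whitney U-test of the difference in response distributions between control (radioembolization alone) and experimental group", with mRECIST treated as ordinal. Section 7.2.1 gives that analysis a "Mann-Whitney U-test to have 85% power to detect a similarly moderately large relative effect of UTMD on the mRECIST score". The next sentence adds the point at issue: "A similar analysis is planned to compare mRECIST evaluations between 1 month and 3-4 month MRI to determine if earlier cross-sectional imaging". Its stated purpose is to learn whether the early scan "can be used to predict long-term treatment response".

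Both scores come from the same patients. The synopsis says "Treatment response will be evaluated using modified response evaluation criteria in solid tumors (mRECIST) at 1 and 3-4 months post treatment", and section 7.2 says "Qualitative findings regarding treatment response will be generated by two radiologists based on mRECIST criteria at 1 and 3-4 months post treatment".

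The plan's other prediction question, Aim 2, is handled differently. The relation of CEUS perfusion to "subsequent mRECIST scores in the UTMD + radioembolization group will be evaluated with" Spearman's rank correlation. No such measure is named for predicting the 3-4-month score from the 1-month score.

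**The concern.** The stated purpose is prediction: does the early score carry information about the same patient's later score? That is a property of the joint distribution of the two scores. A Mann-Whitney test looks only at the two marginal distributions. It cannot tell a perfectly predictive early scan from a useless one if the response categories are equally frequent at both visits. It will also reject when tumours simply go on responding between the scans, however well the early score ranks patients.

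The test also treats the two sets of scores as independent samples, although each patient contributes to both. A paired signed-rank test would repair that but would still measure change. Repeating the arm comparison at 1 month and setting it beside the 3-4-month result would not link the two scores within a patient either.

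What is at stake is interpretation. A non-significant result could be reported as showing that the 1-month scan is sufficient, and a significant one as showing that it is not. Neither follows. Section 1.1 says an earlier predictor would be clinically useful because patients remain eligible for further therapy, so the question deserves an analysis that answers it.

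**Working it through.** **The plan's own figure.** No sample size is stated for this comparison. The Aim 1 figure it leans on reproduces if 0.6 is read as a standardized difference, two-sided: n = 2(1.960 + 1.036)²/0.6² = 49.9 per group. Dividing by the Mann-Whitney efficiency 3/π gives 52.2, and power at 52 per group is 84.8%. The point below does not depend on this.

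**Constructed examples.** The documents give four ordered categories (section 6.5) but no expected response distribution, so the counts are assumed: 52 patients with 20 CR, 18 PR, 9 SD and 5 PD at 1 month. Tests are two-sided; Mann-Whitney is corrected for ties and continuity.

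| 3-4-month score | Spearman | Mann-Whitney p | Signed-rank p |
|---|---|---|---|
| Identical to 1 month | 1.0 | 1.00 | not computable (all differences zero) |
| Same counts, shuffled across patients | 0.00 | 1.00 | 0.83 |
| Same counts, rank order reversed | -0.86 | 1.00 | 1.00 |
| Every non-CR patient improves one category, CR stays CR | 0.82 | 0.00031 | 1.5 × 10⁻⁸ |

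In the first three rows the marginal counts are equal by construction, so U equals its null mean, 52 × 52/2 = 1352, whatever the pairing.

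In the last row the counts become 38/9/5/0:
- U = 1850.5.
- Pooled tie counts are 58, 27, 14 and 5 (N = 104), so the variance is (52 × 52/12) × [105 - Σ(t³ - t)/(104 × 103)] = 19,083 and the SD is 138.1.
- z = (1850.5 - 1352 - 0.5)/138.1 = 3.60, so p = 0.00031.

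**Other assumed counts (CR/PR/SD/PD).**

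| Counts | Reversed: Mann-Whitney p, Spearman | One-category improvement: Mann-Whitney p, Spearman |
|---|---|---|
| 13/13/13/13 | 1.00, -1.00 | 0.00057, 0.95 |
| 31/13/5/3 | 1.00, -0.63 | 0.0047, 0.71 |
| 10/21/16/5 | 1.00, -0.85 | 3.3 × 10⁻⁶, 0.92 |

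**Simulation with sampling variation.** Four-level scores were generated from correlated normal variables for 104 patients, 4,000 runs per scenario. The assumed distribution at 3-4 months is 40/30/20/10%. At 1 month it is either the same or 15/35/40/10%. Rejection rates at 5%:

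| Scenario | Mann-Whitney | Signed-rank | Spearman |
|---|---|---|---|
| Same distributions, no association | 4.5% | 4.6% | 4.9% |
| Same distributions, strong association (mean Spearman 0.87) | 0.0% | 4.3% | 100% |
| Shifted distributions, no association | 95% | 93% | 5.0% |
| Shifted distributions, strong association (mean Spearman 0.84) | about 100% | 100% | 100% |

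Both comparison tests follow the shift. Only Spearman follows the association.

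**Ignoring the pairing.** With the 20/18/9/5 distribution at both scans, the nominal 5% Mann-Whitney test rejects in about 2.3%, 1.0% and 0.20% of trials with 52 pairs at latent within-patient correlations of 0.3, 0.5 and 0.7. With 104 pairs the rates are 2.5%, 1.0% and 0.18%. So the unpaired test is not a sound test of within-patient change either.

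**Precision of the alternative.** For an observed Spearman r = 0.6, z = atanh(0.6) = 0.693 and SE = √[(1 + r²/2)/(n - 3)].
- n = 104: SE = √(1.18/101) = 0.108, 95% CI 0.45 to 0.72.
- n = 52: SE = √(1.18/49) = 0.155, 95% CI 0.37 to 0.76.

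**The case against.** The strongest reply is that the sentence names no test. It sits in a sample-size section after a power statement, so the similarity may refer to non-parametric methods or power in general. An analyst could later choose a cross-tabulation or a rank correlation, and the fault would then be an unnamed method rather than a wrong one. That the test is only implied stands. But the sentence is placed under Aim 1, where the only test described is Mann-Whitney; it speaks of comparing; and Spearman appears only under Aim 2. Followed as written, it leads to the wrong analysis.

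The examples can also be called artificial. Equal margins guarantee p = 1.00, and a uniform one-category improvement will not occur exactly. That is fair: they show what the test can and cannot see and do not forecast this trial's result. The simulation has sampling variation and shows the same behaviour.

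The analysis is ancillary. It is not among the objectives in section 2, and both scores are kept, so the right analysis can be run at any time. This stands and limits the weight of the point.

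Finally, a Spearman coefficient pooled over both arms absorbs any arm effect common to both scans. The size is modest. If UTMD shifts both latent scores by an assumed 0.6 SD, a within-arm latent correlation r becomes (r + 0.09)/(1 + 0.09), where 0.09 = 0.6²/4. That adds 0.08 at r = 0 and 0.03 at r = 0.6. It is a reason to show the result by arm as well, not a reason to keep the comparison. The 104 pairs are also a ceiling, since the scans are clinically scheduled and some may be missing.

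**Conclusion.** The concern holds: as written, the analysis does not answer the question it is planned for. On the natural reading it is a Mann-Whitney comparison of two sets of scores from the same patients, and its p-value reflects a shift between the distributions. Under the assumed distributions it rejects 95% of the time when the early scan carries no information but the distributions shift, and 0% when the early scan is strongly predictive and the distributions match (104 pairs). A signed-rank test or a repeat of the arm comparison at 1 month would not measure prediction either.

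The numbers rest on assumed response distributions because the documents give none. The conclusion does not, since it follows from what the test compares. Confidence is moderate only because the test is implied and not named. The point should be corrected, but it touches an additional analysis: the Aim 1 test, the 52 per group and the data to be collected are unaffected.

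**What to change.** Replace the sentence in section 7.2.1, or move it to section 7.2, with wording such as:

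> Whether 1-month mRECIST predicts 3-4-month mRECIST will be assessed within patients by cross-tabulating the two scores and reporting Spearman's rank correlation with its 95% CI, overall and by arm.

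Optionally add the predictive values of CR/PR at 1 month for CR/PR at 3-4 months, which are easier for clinicians to use. If a signed-rank test is kept, label it as a test of change over time. State how many patients have both scans.

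The cost is one sentence. Both scores are already planned, and no visits, patients or changes to the primary analysis are needed.

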1.1 Background

Hepatocellular carcinoma is the fifth most prevalent cancer worldwide with over half a million new cases reported per year [Alterkruse et al. 2009]. Liver transplant is the only cure for hepatocellular carcinoma, with 70% 5 year survival rates [Mazzaferro et al. 1996]. However, transplant requires a relatively contained disease state (1 lesion 3 < 5 cm or up to 3 nodules < 3 cm) and the technique is limited by availability of donors [Llovet et al. 1999]. Only 30% of referred patients are eligible for surgical resection and this group is still plagued by 5 year recurrence rates higher than 70% [Bruix and Llovet 2002]. Because systemic therapies have been proven largely ineffective, embolization represents the current clinical standard for treatment of non-resectable hepatocellular carcinomas [Llovet and Bruix 2003]. Embolization of HCC can be performed via transarterial chemoembolization or radioembolization. Radioembolization is performed using TheraSpheres (BTG International). TheraSpheres consist of 20-30 µm glass beads containing yttrium-90 isotopes and are FDA approved under a Humanitarian Device Exemption for the treatment of HCC. These spheres are locally delivered via catheter through the hepatic artery to the tumor blood supply and provide a localized and sustained release of radiation. Dosages range from 110-150 Gy and radiation exposure to the surrounding liver is limited by the low penetration of the beta radiation. Yttrium-90 undergoes pure beta emission as it decays to stable zirconium-90 with a half-life of 64 hours and average energy emission of 0.94 MeV. The local beta emissions from this technique have been shown to provide therapeutic effect within the tumor [Herba et al. 1988; Houle et al. 1989]. Post-treatment, localized radioactivity is confirmed via SPECT imaging and patients are monitored for 2-6 hours before being discharged.

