3.1 Trial Duration

Individual participation for patients within the experimental arm will be limited to 3 ultrasound exams. If patients are unable to make one of the 7, or 14 day visits they will still be eligible to participate. The first CEUS exam will take place 1-6 hours post radioembolization during the patient's clinically scheduled observation period. Exams at approximately 7 and 14 days post treatment will take place during separate visits to Thomas Jefferson University. The entire ultrasound imaging protocol will require approximately 90 mins including a 30 min observation period. For patients assigned to the control arm, no additional participation will be required. Patients who receive ultrasound contrast agent will be monitored for at least 30 minutes before being discharged. The research coordinator will obtain laboratory values, imaging data, and outcomes for comparison to the experimental group (all obtained as part of the patient's clinical standard of care). Subject recruitment is expected to last 83 months (March 2017 – December 2023). Analysis and publication of results are expected to take an additional 3 months (January 2024– March 2024). Volunteer Registry Database forms will be submitted to the National Institute of Health's Office of Regulatory Compliance and Quality at the completion of the research study.

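### Pathology is to be tested with the primary endpoint's power, but no tissue collection is planned, so the test would compare subsets formed after randomisation and would not have that power

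*Combined protocol and SAP*

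**What the plan says.** Section 7.2.1 (Sample Size Calculation) sizes Aim 1 on the primary mRECIST comparison and concludes that "a sample size of 52 patients randomized to each group would be needed". The figures behind this are a Mann-Whitney test, 85% power, a type I error of 5% and an effect of 0.6. Still under Aim 1, it continues: "Relative effect sizes for LFT, AFP, pathology, blinded reads from SPECT, planar imaging, and time to next treatment are expected to be similarly large". These endpoints are to be evaluated with non-parametric or exact tests and "are each subject to the same power considerations as for the primary endpoint". The sentence does not spell out a comparison between arms for pathology, but its place under Aim 1 makes that the natural reading.

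Section 7.2.1 is the only place where pathology appears as an endpoint. Section 6.5 (Efficacy Assessments) names mRECIST as the primary measure of tumour response and AFP as the secondary one. No section defines a pathology measure, its timing, its reader, its tissue source or its analysis set.

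No biopsy or other tissue collection appears in Sections 3 (Trial Design), 6.1 to 6.3 (enrolment, screening, imaging) or 6.5. Section 3 says that only outcomes data are collected from controls. Section 3.1 (Trial Duration) adds: "For patients assigned to the control arm, no additional participation will be required". The coordinator gathers laboratory values, imaging data and outcomes from routine care. Section 3 calls the trial open-label, and Section 5.4 says that no blinding will be performed.

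**The concern.** An endpoint can carry the full-sample power only if it is measured in the full sample. Because the study collects no tissue, a patient has post-treatment histology only if a clinician later decides on a procedure that yields some. That decision follows randomisation, may be made with knowledge of the arm, and may depend on how the tumour responded, which is what UTMD is meant to change. Patients with tissue are then not the randomised groups.

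Two things are at stake. First, a non-significant pathology result could be read as evidence of no effect from a test credited with 85% power when its real power may be far lower. Second, a significant result could be read as histological support for the imaging endpoint when it may partly reflect who went on to have a procedure.

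**Working it through.** **1. Reproducing the plan's figure.** Inputs from Section 7.2.1: effect 0.6, power 85%, type I error 5%, Mann-Whitney test. The scale of the effect and the sidedness for Aim 1 are not stated; a standardised difference and a two-sided test reproduce the figure.

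- Two-sample normal formula: n per arm = 2 × [(1.960 + 1.036) / 0.6]² = 49.9.
- Divide by the Mann-Whitney asymptotic relative efficiency, 3/π = 0.955: 49.9 / 0.955 = 52.2 per arm, against the stated 52.
- Power at 52 per arm: effective n = 52 × 0.955 = 49.7, and Φ(0.6 × √(49.7/2) − 1.960) = Φ(2.990 − 1.960) = 84.8%.

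The stated 85% is sound, provided that all 52 patients per arm have the outcome.

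**2. Power for pathology when only a share has tissue.** The documents give no share, so these are assumptions. Power = Φ(0.6 × √(0.955 n / 2) − 1.960):

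| Share with tissue (assumed) | n per arm | Power at 0.6 | Effect detectable with 85% power |
|---|---|---|---|
| 100% | 52 | 85% | 0.60 |
| 75% | 39 | 73% | 0.69 |
| 50% | 26 | 56% | 0.85 |
| 40% | 21 | 48% | 0.95 |
| 30% | 16 | 38% | 1.08 |
| 20% | 10 | 26% | 1.37 |
| 10% | 5 | 15% | 1.94 |

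**3. A real effect with response-linked selection at a common threshold.** Assumptions: tumour kill is N(0,1) in controls and N(0.6,1) with UTMD; tissue is obtained when an imaging score, correlated 0.5 or 0.7 with kill, exceeds one threshold used in both arms; 20-40% overall have tissue; 2,000,000 simulated patients per arm.

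- Raw mean difference among those with tissue: 0.48-0.50 at correlation 0.5, and 0.37-0.40 at 0.7, in SD units of the whole population.
- Selection also narrows the spread: the SD within the subsets is about 0.79-0.91. A rank test responds to the difference relative to that spread.
- On that scale the effect runs from 0.37/0.79 = 0.47 to 0.50/0.91 = 0.55. The loss against 0.6 is 1 − 0.47/0.6 = 22% down to about 9%.
- Availability itself comes to differ by arm: 23% of controls against 37% with UTMD at 30% overall and correlation 0.7.

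**4. No true effect on pathology.** Assumptions: 52 per arm, 3,000 simulated trials, latent-normal selection of the better responders, Mann-Whitney test at 5%.

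| Correlation of availability with response | Availability, control v UTMD | Rejection rate | Mean difference (UTMD − control, SD) |
|---|---|---|---|
| 0 | 30% v 30% | 5.0% | about 0 |
| 0 | 20% v 40% | 4.7% | about 0 |
| 0 | 30% v 50% | 3.9% | about 0 |
| 0.5 | 30% v 30% | 4.3% | about 0 |
| 0.8 | 30% v 30% | 4.6% | about 0 |
| 0.5 | 20% v 40% | 8.8% | −0.22 |
| 0.5 | 30% v 50% | 9.1% | −0.19 |
| 0.8 | 20% v 40% | 21.3% | −0.35 |
| 0.8 | 30% v 50% | 20.4% | −0.29 |

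Under similar assumptions a repeat gave rates as low as 8%, so the range is about 8-21%. Reversing which arm has more tissue reverses the sign. Excess false positives need both conditions: availability linked to response, and availability different by arm.

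**The case against.** The strongest reply is that the documents never say where tissue would come from. A reader might infer that it exists only in patients who later have a transplant or resection. The documents do not support that. Both procedures appear only as general background in Section 1.1, where "transplant requires a relatively contained disease state" describes eligibility in general and donor supply is named as a further limit. The later treatments that the protocol names are chemoembolization and ablation, and a clinically indicated biopsy is not ruled out. This part of the reply stands. It does not rescue the test, because any such clinical source is selected after randomisation.

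A reader might also take the raw differences in step 3 as a loss of 17-39%. That uses the SD of the unselected population; for a rank test within the subset, 9-22% is the relevant loss.

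Nor does it follow that the test must give false positives. With equal availability, or availability unrelated to response, it kept its nominal size in the simulations, and the common-threshold case only weakens a real effect.

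It can also be said that pathology is one word in a list of six supplementary endpoints in a self-described pilot, absent from the objectives and from Section 6.5. That limits the importance, but the sentence still commits to a test and a power level.

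Finally, Section 7.2.1 plans regression for potential confounders. The confounders are not named, and such a model neither repairs selection on a post-randomisation event by itself nor restores the missing patients.

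**Conclusion.** Wrong as written, as regards the power claim. The 85% at 52 per group holds for pathology only if every randomised patient has evaluable tissue, and nothing in the protocol would bring that about. With 20-50% availability, power at 0.6 is about 26-56%.

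The selection problem is conditional. A comparison among patients with tissue is not a comparison of the randomised groups; how much that matters depends on how tissue is obtained, which the documents do not say. Under the assumptions shown, a real effect is weakened by about 9-22%, and the false-positive rate is either about nominal (4-5%) or about 8-21% when availability is both response-linked and different by arm. Every availability share, correlation and selection rule here is an assumption.

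The primary mRECIST comparison does not depend on tissue and is unaffected.

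**What to change.** In Section 7.2.1, remove pathology from the sentence that gives the secondary endpoints the primary endpoint's power. In its place, state that:

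- the number and proportion of all randomised patients in each arm with post-treatment tissue will be reported, with the reason it was obtained;
- pathology will be presented by arm descriptively, labelled exploratory and not as a randomised comparison;
- the pathology measure, its tissue source and its timing are as defined there.

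This is a change of wording only. It adds no procedure and leaves the sample size and the primary analysis as they are. The cost is one secondary p-value, which could not have been read as randomised evidence.

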1.2 Rationale

The fundamental theory behind this study is that localized UCA cavitation within the tumor vasculature will sensitize this tissue to Y-90 radiation and improve patient outcomes. Additionally, we hypothesize that quantification of UCA reperfusion following flash destructive ultrasound pulses will reflect inflammation changes, and provide an earlier predicator of radioembolization treatment response. If UCA

cavitation leads to effective sensitization of HCC to radioembolization, such an approach would improve treatment efficacy and prolong survival. If CEUS-based perfusion measurements were found to accurately predict treatment response, non-responding patients could be identified earlier and scheduled for alternative therapies such as chemoembolization or ablation (which in turn would also prolong survival).

We propose a pilot clinical trial to determine the potential of using CEUS flash-replenishment imaging for improving radioembolization therapy and predicting tumor response. The purpose of this study is to compare tumoral response in 26 patients treated with this approach to 26 patients treated via standard of care (radioembolization alone) and also to determine if quantitative CEUS data acquired from the experimental arm can predict future RECIST outcomes.

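### The adjusted analysis of time to next treatment is assigned to OLS or quantile regression, with no censoring rule and no time-to-event model

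*Combined protocol and SAP*

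**What the plan says.** Time to next treatment appears only in Section 7.2.1, at the end of a list with LFT, AFP, pathology, SPECT reads and planar imaging: "planar imaging, and time to next treatment are expected to be similarly large". These endpoints "will also be evaluated using appropriate non-parametric or exact tests", none of which is named.

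The following sentence deals with adjustment: "potential confounders will be included in ordinary least squares (OLS) regression models (or quantile regression models", the choice between the two "depending on the adequacy of the data meeting OLS modeling assumptions) of these endpoints". The listed endpoints include time to next treatment, and no exception is made for it.

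Section 3.1 sets the calendar. "Subject recruitment is expected to last 83 months", given as March 2017 to December 2023, and "Analysis and publication of results are expected to take an additional 3 months", that is, to March 2024.

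No section defines time to next treatment, gives its start, says how a patient without a next treatment is handled, or names a Kaplan-Meier, log-rank, Cox or other time-to-event method.

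**The concern.** Time to next treatment is known only for patients who have been re-treated. For the others, only a lower bound is known when the data are analysed. Ordinary OLS and ordinary quantile regression need a complete value for each patient. An analyst following the plan would therefore either enter follow-up time as if it were the event time or drop patients not re-treated. The plan does not say which, or how death or transplant counts.

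Both routes shrink the estimated treatment difference. The longest times are the ones cut short or removed, and a beneficial treatment produces more of them in the experimental arm. Section 1.2 points the same way, describing how "non-responding patients could be identified earlier and scheduled for alternative therapies such as chemoembolization or ablation". On that description, patients who respond are the likeliest to have no next treatment.

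Section 7.2.1 also says this endpoint shares the power considerations of the primary endpoint, but gives no number of events. In an open-label trial, leaving the handling of unre-treated patients until the data are in hand is an avoidable post hoc choice.

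**Working it through.** **The plan's own figure.** None is given for this endpoint. The primary calculation says that "a sample size of 52 patients randomized to each group would be needed" for 85% power at an effect of 0.6. Read as a standardised difference with a two-sided 5% test and Mann-Whitney efficiency 3/π, this gives 2 × ((1.960 + 1.036)/0.6)² × π/3 = 52.2 per arm, and power of 84.8% at 52. The figure reproduces on that reading, but it assumes complete outcomes.

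**Follow-up range, from Section 3.1.** The named months, March 2017 to December 2023, span 82 months. A cut at the end of January 2024 gives follow-up of 1 to 83 months. A cut at the end of March 2024 gives 3 to 85 months.

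**Assumptions, not in the documents.** Exponential times; hazard ratio 0.60; uniform accrual; 52 per arm; median months (control v experimental) of 6 v 10, 9 v 15 or 18 v 30.

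**Closed form, unadjusted.** With λ = ln 2/median and censoring time C uniform on (a, b):

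- P(censored) = (e^(−λa) − e^(−λb)) / (λ(b − a))
- E[min(T, C)] = (1 − P(censored)) / λ
- Re-treated only: E[T | T ≤ C] = (E[min(T, C)] − E[C; T > C]) / (1 − P(censored)), where E[C; T > C] = (g(a) − g(b))/(b − a) and g(x) = e^(−λx)(x/λ + 1/λ²)

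Worked case, 9 v 15 months, follow-up 3 to 85:

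- Control: λ = 0.07702, P(censored) = (0.7937 − 0.0014)/(0.07702 × 82) = 12.5%, mean entered = 0.8745/0.07702 = 11.36 months.
- Experimental: λ = 0.04621, P(censored) = (0.8706 − 0.0197)/(0.04621 × 82) = 22.5%, mean entered = 0.7755/0.04621 = 16.78 months.
- True mean difference: 21.64 − 12.98 = 8.66 months. Entered as observed: 16.78 − 11.36, about 5.43 before rounding (63%). Re-treated only: 15.05 − 10.71 = 4.34 (50%).

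| Follow-up (months) | Medians | Censored, control / experimental | True difference | As observed | Re-treated only |
|---|---|---|---|---|---|
| 1–83 | 6 v 10 | 9.4% / 16.4% | 5.77 | 4.22 (73%) | 66% |
| 1–83 | 9 v 15 | 14.6% / 24.6% | 8.66 | 5.23 (60%) | 49% |
| 1–83 | 18 v 30 | 29.2% / 43.8% | 17.31 | 5.92 (34%) | 21% |
| 3–85 | 6 v 10 | 7.5% / 14.2% | 5.77 | 4.36 (76%) | 67% |
| 3–85 | 9 v 15 | 12.5% / 22.5% | 8.66 | 5.43 (63%) | 50% |
| 3–85 | 18 v 30 | 27.0% / 41.8% | 17.31 | 6.22 (36%) | 22% |

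**Simulation of the adjusted models.** Hazard = λ·exp(ln(0.6)·arm + 0.5·z), with z a standard normal baseline covariate (an assumed prognostic strength); 2,500 trials per cell, 500 for median regression. Percentages are of the same model's estimate on complete times.

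| Follow-up (months) | Control median at z = 0 | OLS as observed | OLS re-treated only | Median regression as observed | Cox HR | Power: OLS as observed / re-treated only / Cox |
|---|---|---|---|---|---|---|
| 1–83 | 6 | 63% | 53% | 75% | 0.594 | 52% / 42% / 65% |
| 1–83 | 9 | 50% | 40% | 65% | 0.599 | 45% / 31% / 60% |
| 1–83 | 18 | 28% | 19% | 46% | 0.589 | 34% / 15% / 54% |
| 3–85 | 6 | 67% | 55% | 81% | 0.600 | 53% / 40% / 66% |
| 3–85 | 9 | 52% | 40% | 73% | 0.598 | 48% / 33% / 61% |
| 3–85 | 18 | 29% | 19% | 47% | 0.599 | 36% / 17% / 54% |

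In the 9-month, 3–85 cell, adjusted OLS gives 5.1 months as observed against 9.75 on complete times.

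**No true effect** (median 12 months, equal follow-up, 3,000 trials): OLS as observed rejects in 4.8% at both cuts, Cox in 5.8% and 4.7%. There is no inflation of type I error.

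**The case against.** The strongest reply is that the regression sentence is generic. It sits in a sample-size section and covers endpoints as unlike as AFP and blinded reads, so it can be read as under-specified rather than as choosing a wrong model. Quantile regression also has censored versions. But the sentence does name its models, the only flexibility it allows is a move from OLS to quantile regression, and no censored version is mentioned.

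Several narrower points stand:

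- Medians, hazard ratio, accrual shape and covariate strength are all assumed, so the percentages are illustrative. Their direction is not in doubt: attenuation appears in every cell.
- A January 2024 cut could not supply 3–4 month imaging for the last patients enrolled. Using only 3–85 months changes the ranges slightly, for example 36–76% instead of 34–76%.
- Not all of the power gap between OLS and Cox is due to censoring. In a separate adjusted run at 3–85 months, OLS had 59–61% power on complete times and 38–54% as observed. At the shortest median, about half the gap to Cox is therefore not censoring; at the longer medians most of the loss is. For median regression (300 trials each), power on complete times v as observed was 37% v 37%, 34% v 30% and 41% v 23% from the shortest to the longest medians, so that branch loses much power only at 18 v 30.
- Section 1.2 describes a possible use of early CEUS, and Section 1.1 does not limit later therapy to non-responders. That responders make up most of the censored patients is plausible, not documented.
- The unadjusted wording already allows a log-rank test.

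**Conclusion.** The concern holds, at minor severity. Section 7.2.1 assigns the adjusted analysis of a time-to-event endpoint to models that, as named, cannot take censored times, and nothing elsewhere in the document repairs this. That some patients will lack a next treatment is an inference, since no re-treatment rate is given, but the planned dates leave the last patients about 3 months of follow-up or less.

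Under the stated assumptions, adjusted OLS recovers 28–67% of its complete-data estimate when follow-up is entered as observed and 19–55% when only re-treated patients are kept. Median regression recovers 46–81%. Adjusted Cox returns a hazard ratio of 0.59–0.60 against a true 0.60. With equal follow-up in both arms the consequence is a diluted effect and reduced power. The primary Mann-Whitney test, the 52 per group and the primary power are not affected. Confidence is medium, because the size depends on an unknown re-treatment rate.

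**What to change.** Amend the regression sentence in Section 7.2.1 and add a short definition:

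- Time runs from radioembolization to the first subsequent treatment, and patients not re-treated are censored at last contact. State the data cut date.
- Death is a competing event: report cumulative incidence and fit a cause-specific Cox model. State whether transplant counts as a next treatment or as a competing event.
- The unadjusted comparison uses Kaplan-Meier or cumulative incidence curves with a log-rank test. The adjusted comparison uses Cox regression.
- OLS or quantile regression stays for continuous endpoints such as LFT and AFP changes.

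A composite with death, or restricted mean time, would also be defensible. What matters is that one approach is fixed before the data are examined.

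The cost is a wording change, using standard procedures in the SAS 9.4 already named, and capture of last-contact, death and transplant dates for every patient in both arms. The primary test and sample size do not change.
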